## Analysis Methods

The first re-ablation for each subject will be used for analysis. The number of electrically isolated pulmonary veins will be assessed for each subject and the number of PVs isolated will be compared between randomization arms using a two-sample t-test. It is anticipated that the majority of subjects will have four major pulmonary veins; LIPV, LSPV, RIPV, and RSPV. If a subject has an anatomy in which electrical isolation of more or less than the four major PVs are tested, the number of electrically isolated pulmonary veins for that subject will be normalized to 4.

In addition, a logistic regression model will be fit, to test whether cryo vs RF therapy affect the odds of pulmonary vein reconnection. In the example code below, observations are successes and trials at the subject level, and SAS proc logistic (using trials events syntax) is used. This model assumes similar probabilities of reconnection for all veins within a subject (e.g., reconnection probability is not significantly different between LSPV, LIPV, RSPV, RIPV). This assumption will be tested using frequency tables and Fisher's exact test to assess whether reconnection rates are independent of treatment group by each anatomic location of ablation. This testing will only be performed for locations with 5 or more subjects treated per arm. Odds ratios and corresponding confidence intervals will be back-transformed into probabilities for presentation purposes.

```
proc logistic;
class rand (param = ref ref = 'RF') <other covariates>;
model N_reconnected/N_possible = rand <other covariates>;
run;
```

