**Figure 2.**

## Conclusion of analysis by composition of missing data

## 6.5. Adjustments for Multiple Comparisons

No adjustments for multiple comparisons will be made. All hypothesis tests will be conducted at the nominal 0.05 level of alpha.

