## 7. Determination of Sample Size

The sample size of this study is limited by the number of subjects from the original Fire and Ice trial with repeat ablations who consent to additional data collection. The study objectives are generally descriptive rather than comparative; however, there are hypotheses tests of interest between treatment arms that have an associated type II error and power based on the number of data points included (rate of re-consenting subjects) and effect size. Of particular interest is the hypothesis test of whether the mean number of reconnected pulmonary veins is greater in the RF vs. cryoablation arms (Objective #2; see [section 6.2.2](#)). To demonstrate the ranges of values at which the hypothesis test will be sensitive to between-treatment differences, power for the two-sample t-test was assessed by Monte Carlo simulations ( $10^6$  iterations), assuming a 90% subject reconsent rate, and assuming PV reconnection was binomial with rates of 36.8% for cryo-treated subjects and 58.1% in subjects initially treated with RF ablation (based on published data from Buist et al.). Results are shown below in Figure 3 and in Table 1.

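### The Fisher tests named to check that veins reconnect at similar rates compare cryo with RF within each vein, so they do not test that assumption (supplementary model, Objective #2)

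*SAP*

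**What the plan says.** SAP section 6.2.2 keeps the protocol's two-sample t-test on the number of veins per subject. It then adds a logistic model in which "observations are successes and trials at the subject level". The example code names treatment arm and unspecified covariates, with no vein term.

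The SAP spells out the model's assumption as follows: "reconnection probability is not significantly different between LSPV, LIPV, RSPV, RIPV". It continues: "This assumption will be tested using frequency tables" and Fisher's exact test, the purpose of the latter being "to assess whether reconnection rates are independent of treatment group by each anatomic location of ablation". A minimum count applies: "This testing will only be performed for locations with 5 or more subjects treated per arm". On reporting: "Odds ratios and corresponding confidence intervals will be back-transformed into probabilities for presentation purposes".

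SAP section 6.5 adds: "All hypothesis tests will be conducted at the nominal 0.05 level of alpha". The section does not say what follows if the assumption appears to fail. Protocol section 13.3.2 contains the t-test but neither the logistic model nor this check.

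**The concern.** The assumption is about equality between veins. The Fisher tests are about equality between arms, one vein at a time. The minimum count per arm confirms that each table is arm by reconnection. No test named in the section compares one vein with another.

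A report that followed the text could therefore declare the assumption met or violated on p-values that do not bear on it. A real treatment effect would look like a failed assumption, and large differences between veins could go unremarked by any test. Objective #2 is the comparison that SAP section 7 singles out as of particular interest, so such a statement would be read.

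**Working it through.** The documents give no figure for this check, so there is none to reproduce. The question is how the named tests behave when the assumption is true and when it is false.

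**The two hypotheses.** Write p(a,v) for the reconnection probability in arm a at vein v.
- Assumption: p(a,LSPV) = p(a,LIPV) = p(a,RSPV) = p(a,RIPV) within each arm.
- Fisher null at vein v: p(cryo,v) = p(RF,v).

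Either can hold while the other fails.

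**Inputs.**
- 110 eligible subjects (SAP 6.1.1) and 90% reconsent (SAP 7): 0.9 × 110 = 99.
- Subjects per arm are not stated. Protocol 4.1 gives re-ablation rates of 11.8% of 378 and 17.6% of 384: 0.118 × 378 = 44.6 and 0.176 × 384 = 67.6, a ratio that scales to about 39/60 of 99. Its 49:70 split of re-ablations gives 99 × 49/119 = 40.8 and 58.2. I take 40 cryo and 59 RF as an assumption and vary it.
- Planning rates of 36.8% cryo and 58.1% RF (SAP 7); alpha 0.05 (SAP 6.5), taken as two-sided.
- Vein-specific rates and within-subject correlations are not in the documents. Those below are illustrative assumptions.

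**Assumption true, arms differ.** All four veins are at 36.8% vs 58.1%. The rejection probability of one Fisher test is the sum, over all tables with p < 0.05, of Bin(x; 40, 0.368) × Bin(y; 59, 0.581) = 0.515. Other splits:

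| Cryo/RF | 35/53 | 36/63 | 30/69 | 41/58 | 44/55 |
|---|---|---|---|---|---|
| Rejection | 0.460 | 0.483 | 0.483 | 0.523 | 0.540 |

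**Assumption false, arms equal.** With veins at 20/40/50/70% in both arms, the per-vein rejection probabilities are 0.035, 0.037, 0.040 and 0.037. With every vein at 50% the figure is 0.040. The test responds no more to unequal veins than to equal ones.

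**A test that does address the assumption.** Cochran's Q across the four veins, matched within subject, rejects about 5% in the first case, 100% at 20/40/50/70%, and 87.5–98.5% at a milder 35/45/50/60% (latent correlation 0 to 0.6). The location test in a vein-level model with cluster-robust errors behaves alike: 4–5%, 100% and 86–98%.

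**Effect on the model's estimates.** Without covariates, the fitted probability in each arm is total reconnected veins divided by total veins, whatever the spread between veins. The odds ratio shifts only through non-collapsibility. The vein-level value is (0.368/0.632)/(0.581/0.419) = 0.42. Pooled over veins it becomes 0.43–0.44 at mild spreads (RF veins 35/45/50/60% or 43/53/63/73%) and 0.47–0.50 at wide ones (20/40/50/70% or 20/40/60/80%).

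**Effect on the model's arm test.** Two departures from the binomial variance pull in opposite directions.
- Unequal veins shrink the variance. At 20/40/50/70% the true variance per subject is 0.16 + 0.24 + 0.25 + 0.21 = 0.86, against 4 × 0.45 × 0.55 = 0.99 assumed. The ratio is 0.87, and 2[1 − Φ(1.96/√0.87)] = 3.5%.
- Correlation inflates it. With all veins at 45% and binary correlation 0.13 (latent 0.2), the ratio is 1 + 3 × 0.13 = 1.39, and the same formula gives 9.6%.

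Simulation (20,000 trials) of the events/trials Wald test with no arm effect:

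| Veins | Latent corr. 0 | 0.2 | 0.4 | 0.6 |
|---|---|---|---|---|
| 20/40/50/70% | 3.3% | 6.7% | 10.9% | 14.0% |
| 35/45/50/60% | 4.6% | 9.1% | 13.2% | 17.7% |
| all 45% | 5.0% | 9.3% | 14.0% | 19.1% |

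At small correlations with wide spreads the test stays at or below nominal: 5.0% at latent 0.10 for 20/40/50/70%, and 4.0% for 20/40/60/80%. Across the settings in the table, the vein-level clustered model gives 4.5–4.9% and the t-test 4.8–5.2%.

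**The case against.** The strongest reply is that little depends on this. The model is introduced as an addition, shown as example code and absent from the protocol. SAP section 7 says "The study objectives are generally descriptive rather than comparative". The t-test needs no equal-vein assumption, and the fitted probabilities are not distorted. All of that stands, and it sets the ceiling on severity.

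It is also fair that half of the named check is relevant. Frequency tables by location put the four vein rates side by side, and SAP section 3 leaves room for further analyses. But the SAP promises a test of the assumption, and the only p-values it specifies answer a different question.

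Three stronger readings are tempting and go too far.
- A reader might infer that the check would almost always declare a violation when the planned effect is present. At least one of the four Fisher tests does reject in about 84–95% of simulated trials (latent correlation 0.6 down to 0), but the SAP has no rule that one rejection in four means violation. The figure that needs no such rule is 52% per vein.
- A reader might infer that the model's arm test is always too liberal, or that it is conservative only when veins are independent. Neither holds. The direction depends on both vein spread and correlation, and the documents give neither.
- A reader might infer that the Objective #2 comparison is invalid. The protocol's t-test is untouched.

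A vein-level model is also more than is needed to cure the mismatch alone; relabelling and naming a between-vein test would do that. The case for the larger change is that it removes the correlation problem at the same time.

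**Conclusion.** The point holds and is minor. The named Fisher tests do not test the assumption they are said to test; that follows from the SAP text and needs no calculation. The location tables address it only descriptively, and no consequence of the result is stated.

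The size rests on an assumed split of about 40 and 59 subjects: roughly 52% rejection per vein with equal veins and the planned arm effect (46–54% over the other splits tabulated), and about 4% with widely unequal veins and no arm effect.

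Separately, the events/trials model ignores within-subject correlation, and this check would not show it. Under illustrative vein rates and correlations, its arm test runs from about 3–5% (wide spreads, latent correlation 0 to 0.1) to about 7–9% at 0.2 and 14–19% at 0.6 for the three tabulated patterns.

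**What to change.** 1. In SAP section 6.2.2, stop describing the per-location Fisher tests as a test of equal vein probabilities. Keep them, with the tables, as descriptive arm comparisons by vein.
2. Fit the supplementary logistic model at vein level, with arm and location as terms and robust standard errors clustered by subject (for example GEE). Neither equal veins nor independence within subject is then required. Report its location test as the between-vein comparison.
3. If the events/trials model is kept instead, name one within-subject between-vein test, such as Cochran's Q, as the check, and use a variance that allows for clustering by subject.

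The cost is SAP wording, slightly more programming, and a coding rule for common trunks, additional veins and locations with few subjects. Each vein is already to be classified as isolated or not, so no new data are needed. The protocol t-test does not change.

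### SAP 6.2.2 converts the odds ratio and its confidence interval into probabilities, which an odds ratio alone cannot give; arm-level probabilities should come from each arm's fitted log-odds

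*SAP*

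**What the plan says.** For Objective #2, both the CIP (13.3.2) and the SAP (6.2.2) compare the number of isolated veins per subject between arms with a two-sample t-test. The SAP then adds a second analysis: "In addition, a logistic regression model will be fit, to test whether cryo vs RF therapy affect the odds of pulmonary vein reconnection". The example code makes RF the reference arm, "class rand (param = ref ref = 'RF') <other covariates>", and fits an events/trials model, "model N_reconnected/N_possible = rand <other covariates>".

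On presentation, the SAP says: "Odds ratios and corresponding confidence intervals will be back-transformed into probabilities for presentation purposes". It gives no formula, no reference-arm probability and no covariate values. The covariates are unnamed placeholders, and the code has no statement that produces arm-level probabilities with confidence limits.

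SAP section 7 supplies planning values: "rates of 36.8% for cryo-treated subjects and 58.1% in subjects initially treated with RF ablation".

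**The concern.** The quantities named for conversion are the OR and its confidence interval. An OR compares two odds, and many pairs of probabilities share the same OR. The inverse logit applies to an arm's log-odds, not to a difference of log-odds between arms. In this model the RF log-odds is the intercept and the cryo log-odds is the intercept plus the arm coefficient, both at chosen covariate values. Those two quantities can be turned into probabilities. The arm coefficient alone cannot.

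At stake is how the result reads. A percentage with an interval, shown under an objective about reconnected veins, will be taken for a reconnection rate. If it came from the OR alone, it would be neither arm's rate.

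**Working it through.** **Inputs**
- Per-vein reconnection rates from SAP section 7: cryo 0.368, RF 0.581.
- 110 eligible subjects (CIP 13.1) and about 90% re-consent (SAP 6.4), so 110 × 0.90 = 99 subjects.
- 49 cryo and 70 RF re-ablation procedures (CIP 4.1). The documents do not state re-ablated subjects per arm. *Assumption:* the procedure split applied to 99 subjects, 99 × 49/119 ≈ 41 cryo and 58 RF, with a range of 40/59 to 45/54.
- *Assumption:* four veins per subject, treated as independent, giving 164 cryo and 232 RF veins.

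**Check against the plan's own figures.** The documents give no OR or back-transformed value to reproduce. The planning rate does reproduce the cryo mean under SAP Table 1: 4 × 0.368 = 1.472, stated as 1.47.

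**Step 1: the OR.**
Cryo odds = 0.368/0.632 = 0.582. RF odds = 0.581/0.419 = 1.387. OR (cryo vs RF) = 0.582/1.387 = 0.420; its inverse is 2.381.

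**Step 2: literal back-transform.**
OR/(1+OR) = 0.420/1.420 = 0.296, neither 0.368 nor 0.581. With the arms reversed, 2.381/3.381 = 0.704. An OR of 1 gives 1/2 = 0.50 whatever the common rate is.

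**Step 3: an OR alone fixes no probability.** Cryo probability = OR × RF odds / (1 + OR × RF odds). With the OR held at 0.420:

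| RF rate | Cryo rate | OR/(1+OR) |
|---|---|---|
| 0.20 | 0.095 | 0.296 |
| 0.40 | 0.219 | 0.296 |
| 0.581 | 0.368 | 0.296 |
| 0.70 | 0.495 | 0.296 |
| 0.80 | 0.627 | 0.296 |

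**Step 4: the interval, even with the RF odds supplied.**
Var(log OR) = 1/(164 × 0.368 × 0.632) + 1/(232 × 0.581 × 0.419) = 0.0262 + 0.0177 = 0.0439, so SE = 0.210. The 95% CI for the OR is 0.420 × exp(±1.96 × 0.210), about 0.278 to 0.633.
- Literal transform of those limits: 0.218 to 0.388.
- Limits multiplied by the RF odds (1.387, held fixed), then converted: 0.279 to 0.468.
- Cryo arm's own interval: SE of its log-odds = √0.0262 = 0.162, and the inverse logit of log(0.582) ± 1.96 × 0.162 gives 0.298 to 0.444.

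The converted OR interval is 0.468 − 0.279 = 0.189 wide against 0.444 − 0.298 = 0.146, about 29% too wide. The excess arises because the OR's interval also carries the uncertainty in the RF arm.

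**Step 5: the corrected method.** Inverse logit of each arm's log-odds returns 0.368 (0.298 to 0.444) for cryo and 0.581 (0.517 to 0.643) for RF.

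**Sensitivity.** Across splits of 40/59 to 45/54, the cryo limits move by less than 0.005. The point values in Steps 1 to 3 do not depend on the split or on independence of veins.

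**The case against.** The strongest reply is that the sentence is shorthand. The SAP never writes OR/(1+OR). The model has an RF-reference intercept, standard output prints the intercept and the arm coefficient, and both arms' point probabilities follow from these. The code is offered only as an example, so a missing output statement is not in itself an error. All of this stands. A reader might infer that the report is bound to show 29.6% as the cryo rate, but the documents do not support that: the literal transform is one reading, not a stated formula.

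The shorthand reading does not fully rescue the sentence, because it also converts the OR's interval. Step 4 shows that this fails even when the RF odds are supplied.

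A reader might also infer that this damages the central comparison. The SAP's emphasis is elsewhere: "Of particular interest is the hypothesis test of whether the mean number of reconnected pulmonary veins is greater in the RF vs. cryoablation arms". That describes the t-test on the mean count, which is also the test used for the power calculation. The logistic model is an addition, and section 7 calls the objectives mainly descriptive.

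Finally, the frequency tables by vein location in SAP 6.2.2 and the code review in SAP section 8 could expose an odd percentage. They reduce the risk. They do not correct the rule, and a reviewer checking code against the SAP could pass a literal conversion.

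**Conclusion.** The sentence is wrong as written, and nothing else in the SAP corrects it. An OR and its interval cannot be turned into a probability on their own, and converting the OR's interval through a fixed RF odds does not give the cryo arm's interval. At the SAP's planning rates the literal value is 29.6% against 36.8% and 58.1%. The interval is about 0.28 to 0.47 in place of about 0.30 to 0.44, subject to the assumed 41/58 split and four independent veins per subject.

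The reach is limited. The t-test, the logistic test, the OR, its interval and its p-value do not depend on this sentence, and no conclusion about cryo versus RF changes. What is at risk is a reported reconnection percentage and its interval. Severity is minor to moderate.

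**What to change.** Replace the sentence in SAP 6.2.2 with:

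> The odds ratio and its 95% CI are reported on the odds-ratio scale. Arm-specific reconnection probabilities with 95% CIs are obtained by inverse logit of each arm's fitted log-odds and its confidence limits, at stated covariate values.

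Name the covariates, or state that there are none, so that those values are defined.

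Adapt the example code to match. `LSMEANS rand / ILINK CL` would serve, but in PROC LOGISTIC it needs `param = glm` and will not run under the reference coding now shown. ESTIMATE statements with ILINK work under the current coding. Neither route directly gives a CI for the difference between the two probabilities; that is an optional extra needing its own method and is not part of this correction.

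The cost is one sentence, a small code change and a decision on covariates. No data item, test or objective changes.

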### 6.2.3. Objective #3: Number and location of gaps in pulmonary vein ablation lesions

Summarize the number and location of gaps in pulmonary vein ablation lesions

**Endpoint:** For a redo conducted with a focal catheter and 3D EA mapping, a gap within the pulmonary vein ablation lesion is defined as an electrically reconnected pulmonary vein which after a single spot reablation the response to re-ablation is either PV re-isolation or PV activation-sequence change. Ongoing PV conduction after a single spot re-ablation is attributed to an additional gap. Additional gaps are defined similarly.

For a redo conducted with no 3D EA Mapping, gap location may have been estimated utilizing a mapping catheter. Each gap location will be identified by the classifications provided in **Figure 1**. To define the location of a gap, including the differentiation for spot gap or linear gap, the ipsilateral LA-PV junction is divided into 6 equally distributed segments; superior, antero-superior, antero-inferior, inferior, postero-inferior, and postero-superior. Spot gap is defined as millimeter size, requiring only a single application without moving the catheter. Linear gap (larger continuous gap) is defined by requiring multiple applications or drawing of the catheter.

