7.2. Rationale

Additional procedural re-ablation data will be collected retrospectively of all enrolled FIRE AND ICE subjects who had a re-ablation procedure during the follow-up period.

Within the FIRE AND ICE Trial, the occurrence of a re-ablation procedure, and the energy modality utilized during the procedure (Cryo or RF) were documented, but limited details on the performed re-ablation procedure were captured. Having additional data surrounding the re-ablation procedures may provide insight into the re-occurrence of atrial arrhythmias resulting in a re-ablation procedure.

8. Product Description (N/A)

Retrospective data collection only. No new assessments will be made nor any products used within this project.

9. Selection of Subjects

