9.4. Exclusion Criteria (N/A)

Not applicable. All subjects of whom the additional re-ablation data will be collected are enrollment and valid subjects within the FIRE AND ICE Trial.

10. Study Procedures

No study procedures will be performed under this CIP. Retrospective data will be collected on performed re-ablations occurred during the FIRE AND ICE follow-up period.

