## 6.1.3. Analysis Sets

The full analysis set consists of all subjects who agreed to the additional data collection. The full analysis set will be used for all study objectives.

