## Analysis methods

The number and location of gaps will be presented using summary statistics. Summary statistics are, in this case, frequencies and proportions. Additionally, a contour or density plot may be presented, with higher densities indicating greater numbers of observed reconnections.

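### Do the missing first-re-ablation sentence and the two gap rules leave the gap counts of Objective 3 undefined?

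*SAP*

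**What the plan says.** **Which procedures.** Under Objectives 1, 2 and 4 to 9, both the protocol (13.3) and the SAP (6.2) state: "The first re-ablation for each subject will be used for analysis". Objective 3 (protocol 13.3.3, SAP 6.2.3) has no such sentence. It promises summary statistics for gap number and location, and the SAP adds: "Summary statistics are, in this case, frequencies and proportions". A contour or density plot is optional. No comparison between arms is planned for this objective.

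The general sections do not supply the restriction. SAP 6.1.3 defines the analysis set by subject: "The full analysis set consists of all subjects who agreed to the additional data collection". The opening of protocol section 10 describes the collection in the plural: "Retrospective data will be collected on performed re-ablations occurred during the FIRE AND ICE follow-up period".

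**What is a gap.** For redos with a focal catheter and 3D mapping, a gap is recognised by what a single spot application does: it re-isolates the vein or changes its activation sequence. Then comes "Ongoing PV conduction after a single spot re-ablation is attributed to an additional gap". Further on, the text introduces the six segments of the vein junction with "To define the location of a gap, including the differentiation for spot gap or linear gap". A spot gap takes one application with the catheter held still. By contrast, "Linear gap (larger continuous gap) is defined by requiring multiple applications or drawing of the catheter". The same definitions stand in protocol 6.1.3 and 13.3.3 and in SAP section 4.

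**The concern.** A sentence that appears eight times and is absent once looks either like an oversight or like a deliberate choice to use all re-ablations. Two programmers could produce different tables, and both would comply with the plan. If later re-ablations enter, some subjects count more than once. A gap found at a second redo may also lie in a lesion made at the first redo, possibly with a different energy source from the index ablation. A table split by index arm would then credit that gap to the wrong treatment. The denominator of the proportions is not named either.

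The counting issue touches the endpoint itself. Suppose one continuous gap needs three applications and each changes the activation sequence. The single-spot rule then suggests three gaps, and the linear-gap definition suggests one. A gap closed by drawing the catheter gives no single-spot response to score. Under protocol section 12 the Endpoint Review Committee adjudicates gaps, and neither document tells it in so many words whether a gap that took several applications counts once.

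**Working it through.** The plan gives no figure for Objective 3 that could be reproduced. The check is a short calculation for the procedure set and a reading of the text for the counting rule.

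**Procedure set**

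Inputs: 119 re-ablations in 110 subjects (protocol 13.1); 49 in the Cryo arm and 70 in the RF arm (protocol 4.1); about 90% of eligible subjects expected to re-consent with usable charts (SAP 6.4).

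- Total: 49 + 70 = 119.
- Re-ablations beyond the first: 119 − 110 = 9.
- Share if all subjects are available: 9/119 = 7.6%.
- Subjects at 90%: 0.90 × 110 = 99, so 11 are lost.
- If none of the 11 had a later re-ablation: 99 + 9 = 108 procedures, share 9/108 = 8.3%.
- If the 11 include everyone with a later re-ablation (at most 9 subjects): share 0/99 = 0%.
- Subjects counted more than once: at most 9, which is 9/110 = 8.2%, or up to 9/99 = 9.1% after consent losses.

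The documents do not give the number of re-ablated subjects by arm, so the 9 cannot be split.

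**Counting rule**

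Take one continuous gap closed with k applications in a redo with a focal catheter and 3D mapping.

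| What happens | Single-spot rule | Linear-gap definition, counted once |
|---|---|---|
| Only the last application changes the sequence or re-isolates the vein | 1 | 1 |
| Each application changes the sequence | up to k | 1 |
| Catheter is drawn along the gap | no single-spot response | 1 |

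The first row assumes that persisting conduction makes a further gap only after an application that produced a response. A stricter reading would make every unsuccessful spot a further gap. That would leave almost nothing to be called linear in these redos except gaps closed by drawing the catheter. Protocol section 5 lists the spot/linear distinction among the data to be collected, so that reading is hard to credit.

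The reading that fits all the sentences has two steps: recognise a gap by its response, then record where it lies and whether it is spot or linear. Under it, only the second row leaves the count open.

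The total effect depends on figures the documents do not give. As an assumption, let a share f of gaps be linear, each needing m applications, with every application changing the sequence. The ratio of the two totals is then at most 1 + f(m − 1). For f = 10% and m = 2 it is 1 + 0.1 × 1 = 1.1; for f = 50% and m = 4 it is 1 + 0.5 × 3 = 2.5. With no linear gaps it is 1.0. The spread shows how little can be said; it does not estimate an error.

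**The case for a change.** The case for acting is that the repair is cheap and the moment matters. One sentence in SAP 6.2.3 would fix the procedure set. A counting convention is best agreed before the committee classifies gaps and the database is frozen, since a later correction could mean repeating the adjudication. Objective 2 uses the first re-ablation only, so a gap display built on all procedures would not match it.

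Part of this stands. The sentence is missing from both documents, no general section restores it, and the denominator could be gaps, reconnected veins, junction segments or procedures.

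The rest carries less weight:

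- SAP 6.1.1 defines eligibility by follow-up to a repeat ablation, and protocol 10.11 speaks of the re-ablation procedure in the singular. With eight sibling objectives on the first procedure, an analyst would most likely do the same here. Using all procedures would also be legitimate in a description.
- The harm from crediting a gap to the wrong treatment needs a table by arm that includes later redos, and the Objective 3 text specifies no arm split. The protocol also records in 7.2 that "the energy modality utilized during the procedure (Cryo or RF) were documented", so an analyst who did include later redos could identify the energy used at the earlier one.
- A rule that counts each continuous gap once does not say how to separate one continuous gap from adjacent spot gaps in a past chart, which is where the doubt lies. It would also edit an endpoint definition in the protocol. The relief from amendment in protocol 13.1 is written for analysis methods and may not cover that.
- The gap-location figure is not shown in the text available here, and the case report form is not part of it. Either may already fix the unit. The committee is blinded to therapy group, so its convention cannot be chosen to suit one arm.

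**Conclusion.** No change to the plan follows. The missing sentence is a gap in detail that analysts can fill sensibly, and a table that states its procedures and denominators will show which choice was made. At most 9 procedures are involved, in a descriptive summary where no p-value, power or sample size is at stake.

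The two gap definitions pull against each other in wording but can be read together. The case left open is a continuous gap whose successive applications each change the activation sequence, in the subset of redos with a focal catheter and 3D mapping. How often that occurs is unknown, and it may never occur. It is fair to ask the sponsor how the committee counts such a gap, but the documents show no wrong result that a new sentence would clearly correct.

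This rests on three assumptions: that Objective 3 stays descriptive, as SAP section 7 says the objectives generally are; that the committee applies one convention throughout; and that the re-consent rate is near the 90% the SAP expects. If the gap counts were later used for a formal comparison of the arms, the procedure set and the counting unit would have to be fixed first.
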